7.6 SECONDARY OBJECTIVE ANALYSIS

[figure not shown]
7.6.1 Key secondary objective analysis

[figure not shown]
This section is not applicable as no key secondary endpoint has been specified in the protocol.

[figure not shown]
7.6.2 Secondary objective analysis

[figure not shown]
This section is not applicable as no secondary endpoints have been specified in the protocol.

[figure not shown]

7.8 EXTENT OF EXPOSURE

Extent of exposure will be summarised for the TS in terms of treatment duration, from date of first intake to date of last intake of IMP, ignoring any IMP interruptions. Treatment duration [days] will be calculated as

Treatment duration [days] = Date of last IMP intake – Date of 1st IMP intake + 1.

Treatment duration will additionally be presented in categories showing the number and percentage of participants with treatment duration ≥ 1 day, ≥ 8 days, ≥ 15 days, ≥ 22 days, ≥ 29 days, ≥ 36 days, ≥ 42 days. Additionally, for the BI 1569912 treatment groups, the total dose received will be summarised, calculated from the number of days with IMP taken (i.e. excluding interruptions) and the actual dose per intake as:

$$\text{Total dose [mg]} = \# \text{ days with IMP taken} * \text{actual dose [mg]}$$

IMP interruption data will further be summarised as number of participants with interruptions, total number of interruptions per participant (0, 1, 2, > 2), and reason for interruption (related AE [each PT], unrelated AE [each PT], other). The total number of interruption days per treatment group will also be presented.

Date and time of first and last trial drug administration, IMP interruptions and reasons, calculated treatment duration and total dose will be listed.

7.9 SAFETY ANALYSIS

All safety analyses will be performed on the TS. Analysis will be performed as defined in CTP Section 7.2.6.

7.9.1 Adverse Events

AEs will be coded using the current Medical Dictionary for Regulatory Activities (MedDRA) version in use at Boehringer Ingelheim at the time of (interim) database lock.

The analyses of AEs will be descriptive in nature (see [\[ref. 9.10\]](#), [\[ref. 9.11\]](#)). All analyses of AEs will be based on the number of participants with AEs and NOT on the number of AEs.

CTP Section 7.2.6:

All treated trial participants will be included in the safety analysis and summarised by the actual trial medication received at randomisation. In general, safety analyses will be descriptive in nature and will be based on Boehringer Ingelheim standards. No hypothesis testing is planned.

The analysis of AEs will apply the concept of treatment-emergent AEs (TEAEs). All AEs occurring between first IMP intake and last IMP intake + REP will be considered treatment-emergent. Note that with this definition, TEAEs are all AEs that occur on-treatment, when using the on-treatment definition provided in [Section 6.1](#).

All AEs occurring before first IMP intake will be assigned to ‘screening’ and all AEs occurring after last IMP intake + REP will be assigned to ‘follow-up’. For AEs that start before first IMP intake and deteriorate between first IMP intake and last IMP intake + REP, the deterioration will also be considered ‘treatment-emergent’. For details on the treatment definition and REP, see [Section 6.1](#).

If not otherwise specified, only TEAEs will be included in the AE summaries. In the patient listing of all AEs, non-TEAEs will also be included..

AEs related to hepatic injury (potential severe drug induced liver injury (DILI)) are considered protocol-specified AEs of special interest (AESIs) (see CTP Section 5.2.6.1.4), and are classified as such by the investigator in the eCRF.

For summaries by SOC and PT, the SOC will be sorted by default alphabetically, PTs will be sorted by decreasing frequency (within SOC) in the total column.

An overall summary of AEs will be presented for on-treatment AEs and will be repeated for on-treatment AEs and AEs during follow-up combined.

The frequency of participants with AEs will be summarised by treatment, primary SOC and PT. Separate tables will be provided for participants with:

- Any AE
- Investigator defined drug-related AEs
- Severe AEs
- AESIs
- Serious AEs
- AEs leading to treatment discontinuation

The summary for any AE will be repeated for on-treatment AEs and AEs during follow-up combined.

Tables will include TEAEs only, with the exception of AEs leading to treatment discontinuation, which will include all respective AEs regardless of occurrence relative to IMP end.

According to ICH E3 [[ref. 9.8](#)], in addition to deaths and serious AEs, ‘other significant’ AEs need to be listed in the clinical trial report. These will be any non-serious AE that led to an action taken with study drug (e.g. discontinuation or interruptions [as recorded on the study medication interruption page]). These will also be summarised in an frequency table by SOC and PT.

For disclosure of AE data on ClinicalTrials.gov, additionally the frequency of participants with non-serious AEs occurring in at least 5% (on PT level) of the participants in at least one treatment arm in the TS will be summarised by treatment, primary SOC and PT. There will also be a summary on all-cause mortality.

For disclosure of AE data in the EudraCT register, the frequency of AEs, the frequency of non-serious AEs with an incidence of greater than 5 % (in PT) and the frequency of SAEs will be summarised.

For support of lay summaries, the frequency of participants with drug-related serious AEs will be summarised by treatment, primary SOC and PT.

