A total of 3 active BI 1569912 doses will be administered to provide reasonable coverage for most monotonic shapes of the dose-response relationship. A sufficiently broad set of candidate shapes for this relationship has also been chosen. In addition, an unequal allocation ratio (2:1:1:2) has been selected for the treatment and placebo groups. In general, an allocation of a higher proportion of participants to the placebo and active dose of interest versus other treatment arms will lead to better precision which then leads to a higher power. In addition, increasing the proportion of participants in the placebo group compared with other treatment arms may lead to the observation of a greater separation between the placebo and active treatment arms [[P09-01434](#)]. Details of the statistical approach including the set of candidate models as well as a sample size justification are given in Section [7.5](#).

Data at Week 6 will provide evidence of a sustained effect.

In addition, we will also obtain safety data through the end of observation period (early IMP discontinuation date/EoT +8 days [+6 days]). Collectively, this information will help facilitate the design of pivotal studies.

This trial will include an option for participants to complete questionnaires to provide feedback on their clinical trial experience. Providing this feedback is not required for trial participation, and information collected from these questionnaires will not be analysed as part of the clinical data for the trial (see Appendix [10.1](#)).

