6.2.2.6 EoT Visit

The EoT Visit (at treatment Week 6) represents the regular end of the treatment period. The final IMP intake should occur one day before the EoT Visit. If it is found that a participant has taken the final dose of IMP in the morning of the EoT Visit, the visit should be rescheduled as soon as possible, ideally on the following day. The overall anticipated treatment duration (first IMP intake to the final IMP intake) should be 42 days; therefore, the EoT Visit is scheduled for Day 43 with a visit window of up to +2 days. See Section [3.3.4.1](#) for procedures with regard to premature discontinuation of the IMP.

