7.2.6 Safety analyses

AEs will be coded using the Medical Dictionary for Drug Regulatory Activities (MedDRA). Standard Boehringer Ingelheim summary tables and listings will be produced. All AEs with an onset between start of treatment and end of the REP, a period of 8 days after the last dose of trial IMP, will be assigned to the on-treatment period for evaluation.

All treated trial participants will be included in the safety analysis and summarised by the actual trial medication received at randomisation. In general, safety analyses will be descriptive in nature and will be based on Boehringer Ingelheim standards. No hypothesis testing is planned.

Statistical analysis and reporting of AEs will concentrate on treatment-emergent AEs, i.e. all AEs occurring between the start of treatment and the end of the REP. AEs that start before first IMP intake and deteriorate under treatment will also be considered ‘treatment-emergent’.

Frequency, severity, and causal relationship of AEs will be tabulated by system organ class and preferred term after coding according to the current version of the Medical Dictionary for Drug Regulatory Activities (MedDRA) at database lock.

Laboratory data will be analysed both quantitatively as well as qualitatively. The latter will be done via comparison of laboratory data to their reference ranges. Values outside the reference range as well as values defined as clinically relevant will be summarised. Treatment groups will be compared descriptively with regard to distribution parameters as well as with regard to frequency and percentage of trial participants with abnormal values or clinically relevant abnormal values.

Vital signs, physical examinations, and other safety-relevant data observed at screening, baseline, during the course of the trial, and at the end-of-trial evaluation will be assessed with regard to possible changes compared with findings before the start of treatment.

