6. GENERAL ANALYSIS DEFINITIONS

6.1 TREATMENT(S)

For basic study information on treatments to be administered, assignment of treatment groups, selection of doses, refer to CTP Section 4. The Residual Effect Period (REP) is discussed in CTP Section 1.2 and set to 8 days for this study's analyses.

For statistical analysis, the following analysis phases are defined for each participant:

Table 1: Study analysis phases

Study analysis phase	Label	Start	End ^[1]
Screening	Screening	Date of informed consent	Date/time of first administration of trial drug
On-treatment	Placebo, 5 mg BI, 10 mg BI, 20 mg BI	Date/time of first administration of trial drug	Date/time of last administration of trial drug + REP or 00:00:00 on day after last contact date ^[2] (whichever occurs first)
Follow-up	F/U Placebo, F/U 5 mg BI, F/U 10 mg BI, F/U 20 mg BI,	Date/time of administration of trial drug + REP	00:00:00 on day after last contact date

Note: The defined study analysis phases may or may not exist for a participant. If the derived start of an analysis phase is on or after the derived end of the analysis phase, the phase will be considered missing.

[1] Phases are defined excluding the respective end date/time.

[2] Last contact date is the end of study participation date as recorded on the CRF for most of the patients; if the patient was lost to follow-up, it is the date the patient was last successfully contacted by the site or known to be alive; if the patient died, it is the date of death

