Adherence to time windows will be checked at the last RPM at the latest. Any handling of assessments differing from the described general rules will be documented in the Clinical Trial Analysis Decision Log [[ref. 9.3](#)].

Table 4: Analysis time windows for MADRS, [REDACTED]

Assessments	Label	Target day	Analysis time windows	
			Start	End
MADRS, [REDACTED] [REDACTED]	Pre-dose	1		Day 1, prior to IMP
	Day 8	8	Day 6	Day 9
	Week 2	15	Day 11	Day 22
	Week 4	29	Day 23	Day 36
	Week 6	43	Day 37	
[REDACTED]				
[REDACTED]				

[figure not shown]
Table 5: Analysis time windows for [REDACTED], Safety lab (blood/urine), and vitals

Assessments	Label	Target day	Analysis time windows	
			Start	End
[REDACTED], Safety lab (blood/urine/drug screening), vitals	Pre-dose	1	Day -35	Day 1, prior to IMP
	Day 8	8	Day 6	Day 10

Assessments	Label	Target day	Analysis time windows	
			Start	End
(excluding weight, BMI, height)	Week 2	15	Day 11	Day 22
	Week 4	29	Day 23	Day 36
	Week 6	43	Day 37	Day 47
	Week 8	51	Day 48	
Weight, BMI	Pre-dose	1	Day -35	Day 1, prior to IMP
	Week 6	43	Day 37	Day 47
Height	Pre-dose	1		Day 1, prior to IMP

Table 6: Analysis time windows for ECG

[figure not shown]
Assessments	Label	Target day	Analysis time windows	
			Start	End
ECG	Pre-dose	1	Day -35	Day 1, prior to IMP
	Day 1	1	Day 1, post IMP	Day 1, 23:59
	Day 8	8	Day 6	Day 10
	Week 4	29	Day 23	Day 36
	Week 6	43	Day 37	Day 47
	Week 8	51	Day 48	

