7.9.4 ECG

All ECG summaries will include data from baseline and the on treatment analysis phase.

Abnormal findings will be reported as baseline conditions (at screening) or as AEs (during the trial) if judged clinically relevant by the investigator.

[figure not shown]

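### The end-of-study visit normally falls just after the 8-day residual effect period, so serious, special-interest, severe or drug-related AEs first arising there are left out of their own tables; the ECG text needs reconciling on the same point

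*SAP*

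**What the plan says.** **Phases.** SAP 6.1 states that the REP "is discussed in CTP Section 1.2 and set to 8 days". Its Table 1 ends the on-treatment phase at "Date/time of last administration of trial drug + REP or 00:00:00 on day after last contact date", whichever comes first, and a footnote excludes the end point itself. Protocol 7.2.6 sets the same limit for AEs with onset up to the end of the REP, "a period of 8 days after the last dose of trial IMP, will be assigned to the on-treatment period for evaluation".

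**Visits.** Protocol 6.2.2.6 places the last dose one day before the end-of-treatment (EoT) visit; "therefore, the EoT Visit is scheduled for Day 43", with up to 2 days' allowance. Protocol 3.2 describes observation up to "early IMP discontinuation date/EoT +8 days [+6 days". SAP Tables 5 and 6 give Day 51 as the Week 8 target.

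**AE tables.** SAP 7.9.1 assigns AEs occurring after last dose + REP to follow-up. It plans separate tables for any AE, drug-related AEs, severe AEs, AESIs, serious AEs and AEs leading to discontinuation. Their scope is: "Tables will include TEAEs only, with the exception of AEs leading to treatment discontinuation". The overall summary and the any-AE table are each repeated for on-treatment and follow-up events combined. The patient listing includes events that are not treatment-emergent.

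**ECG.** SAP 7.9.4 says: "All ECG summaries will include data from baseline and the on treatment analysis phase". SAP 6.7 ("Table 6: Analysis time windows for ECG") nevertheless defines a Week 8 ECG window from Day 48. The laboratory and vital signs sections (SAP 7.9.2 and 7.9.3) carry a similar restriction, but each then adds the last follow-up value and its change from baseline.

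**The concern.** EoS is the only scheduled safety visit after EoT. If it normally falls in the follow-up phase, any rule limited to treatment-emergent events or on-treatment data passes over what is first seen there.

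This sits awkwardly with the protocol. Section 5.2.6.1.4 defines the only AESI, potential severe drug-induced liver injury, by laboratory alerts occurring at any time after the first dose, with no REP limit. Section 5.2.6.2.1 requires all AEs and AESIs to be collected to the participant's end of trial. A hepatic alert that first arises in the EoS blood sample is therefore an AESI under the protocol, yet it would not be in the AESI table. If it were also serious, it would be missing from the serious AE table too.

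For ECG, protocol 7.2.6 says that safety-relevant data from the end-of-trial evaluation will be assessed for change from before treatment, and SAP 7.9 says the analysis follows that section. The visible ECG text provides no output that does this for the EoS recording.

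**Working it through.** **Inputs.** Last dose Day 42 and EoT Day 43 (protocol 6.2.2.6); REP 8 days with end point excluded (SAP 6.1, Table 1); EoS at EoT + 8 days with a 6-day allowance (protocol 3.2), or 8 to 14 days after the last dose for early discontinuers who decline further visits (protocol 3.3.4.1).

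**Reproducing the plan's own figure.** EoS target = 43 + 8 = Day 51, which is the Week 8 target in SAP Tables 5 and 6.

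**Gap = EoS day − (last dose day + 8).**

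| Participant | Last dose | REP end | EoS | Gap (days) |
|---|---|---|---|---|
| Completer on schedule | Day 42 | Day 50 | Day 51 to 57 | 1 to 7 |
| EoT on Day 45, EoS counted from actual EoT | Day 44 | Day 52 | Day 53 to 59 | 1 to 7 |
| EoT on Day 45, EoS counted from Day 1 | Day 44 | Day 52 | Day 51 to 57 | −1 to 5 |
| Early discontinuer going straight to EoS | Day d | Day d + 8 | Day d + 8 to d + 14 | 0 to 6 |
| Early discontinuer keeping the schedule, e.g. last dose Day 14 | Day 14 | Day 22 | Day 51 to 57 | 29 to 35 |

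The third row arises because protocol 6.1 counts every visit from Day 1, while protocol 3.2 counts EoS from EoT. The phase ends at a date and time, so a visit with gap 0 is on treatment if it takes place before the clock time of the last dose. A visit with a negative gap is on treatment.

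**Where an AE with onset after last dose + 8 days appears under SAP 7.9.1**

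| Output | Included? |
|---|---|
| Any-AE table, combined version | Yes |
| Overall AE summary, combined version | Yes |
| Patient listing | Yes |
| AEs leading to discontinuation | Yes, regardless of timing |
| Serious, AESI, severe and drug-related tables | No |

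Assignment follows when the event occurs. An event reported at EoS that began inside the REP remains treatment-emergent and stays in all its tables.

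**Laboratory data.** SAP 7.9.2 presents the last follow-up value, its change from baseline, and shifts to it. For a completer the EoS sample is normally that value. It is outside only the worst-value-on-treatment analysis.

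**ECG.** The schedule of assessments has five recordings after the first dose: Visits 2, 3 and 5, EoT and EoS. The EoS recording is one of five. SAP 6.7 gives on-treatment values priority in the windows from Day 1 to Week 6 and does not list Week 8, which suggests that Week 8 was meant to hold follow-up data. That does not fit a restriction of all summaries to baseline and on-treatment data.

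**The case against.** The strongest reply is that limiting category tables to events within a residual effect period is a declared choice, consistent between protocol 7.2.6 and SAP 6.1 and 7.9.1. Protocol 1.2 gives a terminal half-life of about 4 hours, so 8 days is 8 × 24 / 4 = 48 half-lives, and later onsets may well have little to do with the drug. This stands as an argument for keeping the REP; its rationale is redacted and cannot be judged here. It does not explain why the any-AE table is extended to follow-up while the serious and AESI tables are not.

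Four stronger readings are tempting and are not supported:

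- **That these events are lost from the report.** They appear in both combined outputs and in the listing, and SAP 7.9.1 also provides for listing serious AEs under ICH E3. The visible text does not say whether the overall summary has rows for serious, severe or special-interest events.
- **That every EoS visit is off treatment.** The table above shows boundary cases.
- **That EoS ECGs are summarised nowhere.** The SAP contents list puts 7.9.4 on page 47 and Section 8 on page 50, and only a few lines of 7.9.4 are visible. Follow-up ECG outputs may be in text that is not shown. In the laboratory and vital signs sections, nearly the same restricting sentence is followed by follow-up values. A clinically relevant ECG finding would also be reported as an AE.
- **That the category tables drive dose selection.** Protocol 7.2.3.1 and SAP 7.5.1 refer to the totality of evidence.

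**Conclusion.** The AE point holds as a gap in presentation. For a completer on schedule, EoS comes 1 to 7 days after the on-treatment phase closes. For an early discontinuer going straight to EoS the gap is 0 to 6 days, and for one who keeps the visit schedule it is longer. A few boundary visits may remain on treatment. Serious, special-interest, severe and drug-related AEs with onset after last dose + 8 days are absent from four category-specific tables and present in the two combined outputs and the listing. The number of such events cannot be estimated from the documents and may be small.

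The ECG point holds only as a conflict to resolve, between SAP 7.9.4 as visible on one side and SAP Table 6 and protocol 7.2.6 on the other. If no follow-up summary exists, one of the five scheduled recordings after the first dose would normally go unsummarised.

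Both conclusions assume the dosing and visit days in the protocol are followed. The first is worth acting on because it concerns protocol-defined AESIs and serious AEs missing from the tables that carry their name, and the correction is cheap.

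**What to change.** 1. **SAP 7.9.1:** repeat the serious, AESI, severe and drug-related AE tables for on-treatment and follow-up AEs combined, in the format already planned for any AE. Keep the treatment-emergent versions and leave the REP unchanged.
2. **SAP 7.9.4:** reconcile its scope with the Week 8 window in Table 6 and with the end-of-trial assessment in protocol 7.2.6. If no follow-up ECG summary exists, add the last follow-up value and its change from baseline, as for laboratory data and vital signs.

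The cost is SAP wording and about five outputs (four AE tables and one ECG summary), with no new data. The small downside is that some late events unrelated to treatment will appear in the combined tables; showing them beside the treatment-emergent versions keeps the distinction clear. The change should be made before unblinding.

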7.9.2 Laboratory data

The analyses of laboratory data will be descriptive in nature and will be based on Boehringer Ingelheim standards [ref. 9.12]. All summaries will include data from baseline and the on-treatment analysis phase. Safety laboratory parameters to be assessed are listed in CTP Table 5.3.4:1.

Data will be received from a central laboratory; the respective reference ranges will be provided in the investigator site file.

CTP Section 7.2.6: *Laboratory data will be analysed both quantitatively as well as qualitatively. The latter will be done via comparison of laboratory data to their reference ranges. Values outside the reference range as well as values defined as clinically relevant will be summarised. Treatment groups will be compared descriptively with regard to distribution parameters as well as with regard to frequency and percentage of trial participants with abnormal values or clinically relevant abnormal values.*

Descriptive statistics of laboratory values over time and for the difference from baseline will be provided (based on selected values within analysis time windows as specified in Section 6.7.). In these summaries, also the last value in follow-up as well as the change from baseline to last value in follow-up will be presented.

Frequency tables of shifts from baseline to last value on treatment, worst value on treatment and last value in follow-up will be presented. Worst value will be defined and analysed separately for worst low and worst high values (where applicable, with respect to the respective reference range).

Number and percentage of participants with possibly clinically significant abnormalities (low/high) will be presented per lab parameter.

Clinically relevant findings in laboratory data will be reported as baseline conditions (prior to first administration of trial drug) or as AEs (after first administration of trial drug) if judged clinically relevant by the investigator, and will be analysed as such.

Quantitative analyses will be based on normalised values, which means transforming to a standard unit and a standard reference range, see [ref 9.12]. The original values will be analysed if the transformation into standard unit is not possible for a parameter.

